2.2.2 Study Design Schematic

2.3 Subject Selection:

2.3.1 General characteristics of the proposed subject population

Similar to prior studies conducted on GAE, subjects included in the study will be those with mild to moderate knee osteoarthritis with moderate to severe pain that is refractory to conservative management. These are patients who have significant symptoms but are not ideal candidates for total knee replacement.

2.3.2 *Anticipated number of research subjects*

For the Pilot Study, 30 patients are expected to enroll (defined as completion of the informed consent process as per University IRB policies) and all are expected to complete the study.

2.3.3 Inclusion Criteria:

1. Patients between ages 18 and 75 with moderate/severe knee pain secondary to primary osteoarthritis. Moderate/severe pain will be defined as pain 30 mm to

100 mm on the Visual Analog Pain Scale (where 0 denotes 'no pain' and 100 mm denotes worst pain imaginable')

- 2. Grade 1, 2, or 3 osteoarthritis on the Kellgren-Lawrence grading scale on knee x-ray in the last 12 months
- 3. Pain must be refractory to 3 months of medical management (which may include a combination of oral analgesics, intraarticular steroids, viscosupplementation, opioid therapy, etc)
- 4. Patients willing and able to consent to the study

2.3.4 Exclusion Criteria:

- 1 Kidney dysfunction defined as an estimated GFR < 60 mL/min
- 2 Acute knee injury
- 3 Current local infection
- 4 Prior ipsilateral knee replacement surgery
- 5 Infectious or inflammatory arthritis
- 6 History of contrast allergy resulting in anaphylaxis
- 7 INR (International Normalization Ratio) > 1.6
- 8 Platelets < 50,000
- 9 Significant atherosclerosis that would limit angiography
- 10 Active malignancy
- 11 Active pregnancy
- 12 Appropriate candidate for knee replacement surgery determined by clinical and physical examination
- 13 Recent within 3 months, or active cigarette user
- 14 Any other condition that in the opinion of the investigator would preclude the patient from participation.

2.4 Study Procedures:

2.4.1 Patient Recruitment:

Patients will be recruited from sports medicine, family medicine, orthopedic, geriatric, and rheumatology clinics. Participating clinicians and research partners will identify patients with moderate or severe pain secondary to primary osteoarthritis (using the Kellgren-Lawrence Scale) who have persistent knee pain refractory to all attempted medical therapies and lifestyle modifications. The clinician will notify one of the GAE research team members. The patient will then be scheduled for consultation in the Interventional Radiology (IR) clinic. A thorough description of the research study will be provided. Informed consent will also take place at this time (see below). Once the bloodwork and imaging are reviewed, the patient will be scheduled for the procedure following this clinic visit if they meet criteria and the patient is willing to proceed.

Visit 1 - Screening:

The screening period may take up to 8 weeks to complete. Some of the tests and assessments will be performed at the time of the consultation in Interventional Radiology (IR). Other tests and assessments

will be scheduled at appropriate facilities within the 8-week period. The following will be performed for screening:

- 1) Obtain informed consent
- 2) Collect demographics including age, sex, and race
- 3) Medical history and co-morbidities
- 4) Physical exam to include height, weight, BMI and vital signs
- 5) Evaluation for moderate sedation
- 6) Knee MRI with or without contrast. If performed within 12 months will not need to be repeated. Knee injury and Osteoarthritis Outcome Score (KOOS) questionnaire
- 7) Frequency/dosage of analgesic questionnaire
- 8) 100 mm visual analog pain scale
- 9) Knee x-ray. If performed within 12 months will not need to be repeated.
- 10) 30 second chair stand test
- 11) Pre-procedure labs If performed within 1 month will not need to be repeated:
 - CBC with Platelets
 - o GFR
 - o INR
 - o PTT

Pregnancy test for women of child-bearing potential

Remote consenting may be used as opposed to in person consenting where possible to reduce unnecessary in person encounters. In the event remote consenting is utilized, subjects will be provided with a copy of the informed consent prior to the teleconsent meeting either via email, fax, mail or previously provided during an in-person visit. After the physician investigator and subject review the consent form via video conferencing (e.g., telephone, conference call, videoconference, telemedicine, etc.), the subject will be offered the opportunity to ask any questions and have those questions answered. The subject will sign and date the informed consent.

The physician investigator will verify the subject physically signed the consent document either by viewing via video conference or obtaining a photo of the complete signed consent signature page or obtaining verbal confirmation from the subject that he/she signed the consent form or agreed to participate electronically. The signed document is then mailed, emailed, photo/scanned to text or faxed to the study team.

If the signed consent is provided as an electronic copy (emailed, photo/scanned, or faxed), the subject will return the original signed document on their first in person visit or by mail. If the signed consent form is mailed to the study team, the physician investigator will sign their copy which they possess after the subject has acknowledged signature on their copy. Once the subject's original copy is received the study team's copy will be attached to make a single document.

The study team will document the remote consent process, including the date and time the conversation occurred, how it occurred (e.g., telephone, video conference), the names of the participants, confirmation that the subject received the informed consent, and confirmation of informed consent to participate.

Visit 2 GAE Procedure:

Subjects should withhold pain medication 24 hours prior to visit for the evaluation of VAS or other measures.

Subjects will be treated with a genicular artery embolization (GAE) procedure performed with Gel Bead Microspheres. The microspheres will be delivered in a saline-contrast medium solution and will be delivered to the arteries supplying the areas of the subject's pain.

Subjects will not initiate new pain therapy or escalate current therapy for 1 month prior to GAE. A dose of intravenous antibiotic will be given in the peri-procedural period and oral antibiotics may be continued for up to 7 days. Anti-inflammatory medications will also begin 1 day prior to and up to 7 days after the procedure.

On the day of the procedure, the subject will be brought to the angiography suite and positioned in the supine position. Anxiolytic medications and analgesics will be administered per patient and provider discretion. After appropriate local anesthesia, arterial access will be obtained using a standard micropuncture kit. The femoral artery ipsilateral to the affected knee will be catheterized. A subsequent angiogram will be used to identify abnormal neovascularization arising from the geniculate artery branches. The affected geniculate artery branches will be catheterized with a microcatheter and the abnormal vessels will be embolized with a suspension of the Gel-Bead particles ranging in size from 100 to 500 micrometers at the physician's discretion. The suspension will slowly be injected into the vessel until there is stasis of forward flow. All guidewires, catheters and microcatheters will be removed. Hemostasis will be obtained either with manual compression or a closure device.

The following data will be collected during each GAE procedure:

- Technical success of GAE, defined as successful catheterization and embolization
- Procedure time, duration of hospitalization, duration of catheterization, fluoroscopy dose, volume of embolic delivered, arteries embolized.

Post-procedure Care and Disposition:

Following the procedure, the patient will be observed in the post-procedure area. Routine postangiography care will be provided and routine precautions followed (lying flat for up to 6 hours post procedure, adequate post-procedure hydration with intravenous fluids). No additional lab work will be routinely drawn at this time. Any additional labs drawn will be left to the discretion of the attending physician. All complications, minor and major, will be documented and managed appropriately at the physician's discretion. Patient may be deemed appropriate discharge on the same day if:

- 1. There are no access site complications (e.g. groin hematoma)
- 2. Pain is adequately controlled
- 3. Patient is ambulatory
- 4. Distal perfusion to the bilateral lower extremities is confirmed by physical examination and/or Doppler waveforms
- 5. There are no signs of active bleeding or hemorrhage
- 6. Patient has a safe ride home

After GAE, follow-up will occur at 1 week (\pm 4 days), 1 month (\pm 2 weeks), 3 months (\pm 2 weeks), 6 months (\pm 2 weeks) from the date of treatment.

Visit 3 - 1 week (± 4 days) Post Procedure Phone Call

One week after the GAE procedure, a phone follow-up call will be made to check the on status of the subject. Standard post surgical questions pertaining to infection and pain will be asked. If there are any concerns, an in-person evaluation will be scheduled.

Visit 4 - 1 month (± 2 weeks) Post Procedure

Subjects will have the following assessments performed:

- Physical examination including vital signs
- KOOS and VAS questionnaires
- 30 second chair stand test
- Review of adverse events

Visit 5 - 3 months (± 2 weeks) Post Procedure

Subjects will have the following assessments performed:

- Physical examination including vital signs
- KOOS and VAS questionnaires
- 30 second chair stand test
- Review of adverse events

Visit 6 - 6 months (± 2 weeks) Post Procedure

Subjects will have the following assessments performed:

- Physical examination including vital signs
- KOOS and VAS questionnaires
- 30 second chair stand test
- Review of adverse events

Whenever possible, follow-up phone calls\tele-medicine visits will be made to subjects at 12 and 24months post procedure to obtain updated information on pain.

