Study Title: Geniculate Artery Embolization for the Treatment of Knee Osteoarthritis 04/08/2025

G190248 Supplement 001

A. Cover Page

Device Information : Device name: Teleflex Gel-Bead

Intended use of device:

The Gel-Bead embolization particles will be used to perform geniculate artery embolization (GAE) for the purposes of treatment of osteoarthritis-related knee pain.

Device Information:

Device name: Teleflex Gel-Bead

Intended use of device:

The Gel-Bead embolization particles will be used to perform geniculate artery embolization (GAE) for the purposes of treatment of osteoarthritis-related knee pain.

Sponsor-Investigator and Correspondent Contact Information:

[name] University of Pittsburgh Medical Center [name] [contact] / [contact] [contact]

Manufacturer Information:

Teleflex (acquired Vascular Solutions, Inc. February 2017) [name] [contact]

Distributed by Medtronic

Referenced files: There are no referenced files.

Protocol Ammendments:

Updated protocol to remove 6-minute walk test due to feasibility issues in performing

B. Clinical Plan

The primary goal of our investigation is to determine if geniculate artery embolization (GAE) will result in a decrease in pain and disability caused by knee osteoarthritis. The investigation will be conducted as two distinct studies:

 A pilot study of GAE for the treatment of knee osteoarthritis
 A series of up to 30 subjects undergoing geniculate artery embolization will be included in this arm with the explicit purpose to demonstrate safety and efficacy.

The primary endpoint of this study is overall efficacy of treatment as determined by a minimal clinically significant improvement in KOOS pain score of 10 based on the KOOS Pain questionnaire at 6 months.

Secondary outcomes will be improvement in functionality and quality of life based on the KOOS Function in Sport and Recreation, and KOOS Quality of Life Scales. Secondary outcomes will also include changes in quantitative functional metrics as well as reduction in medication use.

Technical success will be defined as the performance of diagnostic angiography of the knee with delivery of the Gel-Bead particles to a region of hypervascularity within the knee resulting in reduced flow/occlusion of the target vessels. Clinical success will be defined by a decrease in pain of 10 points per the KOOS questionnaire at 6 months.

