1.1 Trial Objective

The purpose of this study is to perform a pilot to determine efficacy of transcatheter arterial embolization of the geniculate arteries in treating knee osteoarthritis related pain using the Gel-Bead embolization particles. This trial will assess reduction in pain, functional improvement, and reduction of medication usage in patients with mild to moderate knee osteoarthritis who have failed conservative management.

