2.2.1 General Study Design

A series of 15 patients undergoing geniculate artery embolization will be included in this arm with the explicit purpose to demonstrate safety and efficacy.

This trial will assess reduction in pain, functional improvement, and reduction of conservative medical therapy in patients with mild to moderate knee osteoarthritis who have failed conservative

management, for 6 months and for up to two years following embolization.

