2.5.1.2 Secondary Endpoints

Secondary outcomes will be improvement in functionality and quality of life based on the KOOS Function in Sport and Recreation KOOS, and Quality of Life Scale at 6 months as well as the quantitative functional measures and changes in medication use. To adjust for multiple comparisons, the Holm-Bonferroni correction method will be implemented.

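### Change in medication use is an objective and a secondary endpoint, but the visit text lists the analgesic questionnaire at screening and at none of Visits 4, 5 and 6

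*Combined protocol and SAP*

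**What the plan says.** Section 1.1 sets out three things the trial will assess: "reduction in pain, functional improvement, and reduction of medication usage". Section B repeats the third as an outcome: "Secondary outcomes will also include changes in quantitative functional metrics as well as reduction in medication use". Section 2.5.1.2 includes it among the secondary endpoints, after the KOOS scales at 6 months: "as well as the quantitative functional measures and changes in medication use". The general design text in section 2.2.1 has a close variant: "reduction in pain, functional improvement, and reduction of conservative medical therapy".

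In section 2.4.1, the Visit 1 screening list contains KOOS, the item "Frequency/dosage of analgesic questionnaire", a 100 mm VAS and the 30-second chair stand test. Visits 4, 5 and 6 (1, 3 and 6 months) share one four-item list: physical examination with vital signs, "KOOS and VAS questionnaires", the chair stand test and a review of adverse events. The analgesic questionnaire is not named again anywhere in the document.

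Section 2.4.2.1 (Study Compliance) adds that conservative treatment, current and prior, is to be reviewed with each subject at follow-up visits. Subjects who significantly escalate treatment are to be withdrawn. Section 2.5.3 plans paired t-tests of baseline against endpoint scores for the pilot group.

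**The concern.** A change score needs the same quantity measured at both ends. The visit text provides a baseline for analgesic dose and frequency but states no matching measurement at any later visit. A site that follows the lists exactly would reach 6 months with a baseline form and nothing to set against it. Change in medication use would then rest on whatever the compliance review happened to record.

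This is more than a missing detail of analysis. A late analysis plan can define a score or choose a test, but it cannot supply a dose and frequency that were not recorded at the visit. Afterwards the only sources are recall and chart abstraction.

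**Working it through.** The plan gives no figure on this point, so there is nothing to reproduce. The check is a comparison of the endpoint text with the assessments listed at each scored visit.

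**Step 1: what the endpoint needs.** Sections 1.1, B and 2.5.1.2 call for change, or reduction, in medication use. Section 2.5.3 compares baseline with endpoint by paired t-test. For each subject, the paired difference is

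d = (value at 6 months) − (value at baseline),

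with both values on one scale. The only scale named for medication use is the frequency and dosage questionnaire.

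**Step 2: where each outcome instrument is listed (section 2.4.1).**

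| Instrument | Visit 1 | Visit 4 | Visit 5 | Visit 6 | Follow-up count |
|---|---|---|---|---|---|
| KOOS | yes | yes | yes | yes | 3 of 3 |
| VAS | yes | yes | yes | yes | 3 of 3 |
| 30-second chair stand | yes | yes | yes | yes | 3 of 3 |
| Analgesic questionnaire | yes | no | no | no | 0 of 3 |

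The other three instruments fill 3 × 3 = 9 of 9 follow-up slots. The analgesic questionnaire fills 0 of 3, and 0 of 1 at Visit 6. It is the only one of the four screening instruments that does not return.

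**Step 3: whether the compliance review can stand in.** The section 2.4.2.1 review takes place at follow-up visits and concerns conservative treatment, so it overlaps with the endpoint. It differs in two ways.

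- Purpose: it looks for escalation, and the stated consequence is withdrawal. The endpoint concerns reduction. A reviewer can correctly record that there was no escalation for a subject who halved the dose and for one who changed nothing.
- Content: it names no dose, frequency, form or recall period. Its output is not on the questionnaire's scale, so d in step 1 cannot be formed from it as specified.

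**Step 4: number of forms needed to close the gap.** The document gives 15 subjects (sections 2.2.1, 2.5.2 and 3.1) and 30 (section 2.3.2; up to 30 in section B), so both are used.

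- Visit 6 only: 15 × 1 = 15, or 30 × 1 = 30.
- Visits 4, 5 and 6: 15 × 3 = 45, or 30 × 3 = 90.

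**The case against.** The best reply is that follow-up on treatment is already provided for. Inclusion criterion 3 in section 2.3.3 describes medical management as possibly including oral analgesics, intra-articular steroids and opioids, so a review of conservative treatment plausibly covers medication. The review is not on the Visit 4 to 6 lists either, which shows that those lists are not exhaustive; absence from a list is therefore not proof that nothing is done. In addition, the schematic under section 2.2.2 is not shown, and a visit schedule there might include the form. Finally, this is one secondary endpoint in a small single-arm pilot.

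Much of this stands. A reader might infer that no medication information is collected after baseline. Section 2.4.2.1 contradicts that. What remains is narrower: no follow-up dose or frequency measurement comparable with baseline is specified. If the schematic does show the questionnaire, the visit text still needs to agree with it.

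A reader might also count every later contact, including the 1-week call and the 12- and 24-month calls, since section 2.2.1 speaks of assessment "for 6 months and for up to two years following embolization". That would overstate the gap. Section 2.5.1.2 frames the secondary endpoints at 6 months. The 1-week call falls during or just after an anti-inflammatory course that may run for up to 7 days. The two long-term calls are made only where possible and are for updating pain. None of these contacts serves the 6-month endpoint.

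**Conclusion.** The point holds in this form: in the visit text, a stated objective and secondary endpoint has a baseline instrument and no listed follow-up measurement on that instrument, at 0 of 3 scored follow-up visits against 3 of 3 for each of the other three. The compliance review would yield some medication information, but not a paired value on the baseline scale. It should be corrected, because the loss cannot be repaired at analysis and the correction is small.

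The conclusion rests on three conditions. It is limited to the visit text, because the schematic is not available. It assumes sites collect what the visit lists and section 2.4.2.1 specify and no more. It also reads the 6-month time point in section 2.5.1.2 as covering medication use, although the sentence attaches it most directly to the KOOS scales.

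A reader might go further and infer that the KOOS Pain result is biased by unmeasured changes in analgesic use. The documents do not support that: they give neither a size nor a direction for any such change. The primary endpoint remains measurable as listed.

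**What to change.** Add the existing frequency and dosage questionnaire to the Visit 6 list in section 2.4.1, and preferably to Visits 4 and 5, so that medication use follows the same schedule as KOOS, VAS and the chair stand test. If the schematic carries a schedule of assessments, make it match.

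For follow-up visits already completed, abstract what the section 2.4.2.1 review recorded. Report it as abstracted information, separate from questionnaire values.

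The cost is a short amendment to between one and three visit lists, with no new instrument: 15 to 30 extra forms if only Visit 6 is changed, or 45 to 90 if all three visits are, at a few minutes each.

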2.4.2.1 Study Compliance

Subjects will be required to avoid escalation of conservative therapy during the study period. A review of current and prior conservative treatment measures will be reviewed with each subject during follow-up visits. Any patient that significantly elevates conservative therapy (e.g. initiation of a new medication or therapy not previously used) will be withdrawn from the study.

Early Withdrawal of Subjects:

Subjects will be withdrawn from the study under the following conditions:

- 1 At any point at the patient's discretion
- 2 Any major complication that occurs that prevents the ability to perform/complete the GAE procedure
- 3 Patient is unable to complete at least one follow-up visit

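### Change in medication use is an outcome, but escalation is forbidden and significant escalation leads to withdrawal, so the before-after comparison is biased towards a reduction and can show one even if embolization does nothing

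*Combined protocol and SAP*

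**What the plan says.** **Medication as an outcome.** Section 1.1 states: "This trial will assess reduction in pain, functional improvement, and reduction of medication usage". Section B (Clinical Plan) uses the same one-directional wording: "Secondary outcomes will also include changes in quantitative functional metrics as well as reduction in medication use". Section 2.5.1.2 is neutral and lists "quantitative functional measures and changes in medication use". No unit, scale or test for medication use is defined.

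**Limits on increases.** Section 2.4.2.1 gives a general instruction, "Subjects will be required to avoid escalation of conservative therapy during the study period", and a consequence: "Any patient that significantly elevates conservative therapy (e.g. initiation of a new medication or therapy not previously used) will be withdrawn from the study". No threshold defines a significant rise. The list of withdrawal conditions further down the same section does not include escalation, so the two parts need reconciling. Before treatment, the Visit 2 text in Section 2.4 adds: "Subjects will not initiate new pain therapy or escalate current therapy for 1 month prior to GAE". No section restricts reductions.

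**Analysis.** Section 2.5.3 compares baseline and endpoint scores in the pilot group by paired t-test. Section 2.5.1.1 writes a hypothesis against sham, but the design and enrolment sections describe a single treated group. No section says how a patient withdrawn for escalation enters the medication analysis.

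**Measurement.** The analgesic questionnaire is listed at screening but not at the 1-, 3- or 6-month visits. For follow-up, Section 2.4.2.1 provides only a review of conservative treatments.

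**The concern.** Comparing medication change with zero assumes that, without a treatment effect, use is as free to rise as to fall. Here it is not. Rises are limited twice:

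- **By instruction.** A patient who would have taken more but obeys the rule is recorded as unchanged.
- **By withdrawal.** A patient who starts a new therapy leaves the study and may leave the analysed set.

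Both push the average change towards a reduction, which is the result named in the objective. With one arm, there is no comparison group under the same rule to cancel the bias. At stake is a fall in medication use being reported as a benefit of embolization, and as support for the pain result, when the compliance rule produced some or all of it.

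**Working it through.** The documents give no figure for medication use, so there is none to reproduce. The power stated in Section 2.5.2 concerns KOOS Pain and is not an input.

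**Inputs from the documents.** The number of patients is 15 (Sections 2.2.1, 2.5.2, 3.1) or 30 (Section 2.3.2; Section B says up to 30), so both are shown.

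**Assumptions.**
- Embolization has no effect on medication use.
- Each patient's change is −1 (down), 0 or +1 (up). Without the rule, a share p would go down and the same share p would go up. Values of 5%, 10% and 20% are tried.
- The test is a paired t-test at two-sided 0.05. Section 2.5.3 names that test only for scores, two-sidedness is stated only for the primary endpoint, and 0.05 only for adverse events.

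**Bias in the mean change.**
- All increasers removed: −p/(1−p), which is −0.053, −0.111 and −0.250 at p = 5%, 10% and 20%.
- Half of increasers removed: −(p/2)/(1−p/2), which is −0.026, −0.053 and −0.111.
- All increasers comply and are recorded as unchanged: −p, which is −0.05, −0.10 and −0.20.

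**When the test calls this significant.** With k patients analysed, d reducers and no increasers, the mean is −d/k and the variance is d(k−d)/(k(k−1)). Hence |t| = √(d(k−1)/(k−d)).
- k = 15: d = 3 gives √(3×14/12) = 1.87 and d = 4 gives √(4×14/11) = 2.26. The critical value is 2.145.
- k = 30: d = 3 gives √(3×29/27) = 1.80 and d = 4 gives √(4×29/26) = 2.11. The critical value is 2.045.

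Four reducers are enough at either size, and also at the smaller k left after removals (checked at 12, 24 and 27). The false-reduction rate with all increasers removed is therefore P(Binomial(n, p) ≥ 4). The other rows come from enumerating all outcomes.

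| Trials showing a significant reduction, no true effect (n = 15 / n = 30) | p = 5% | p = 10% | p = 20% |
|---|---|---|---|
| No restriction | 0.3% / 1.5% | 1.6% / 2.4% | 2.4% / 2.2% |
| Half of increasers removed | 0.4% / 3% | 3% / 9% | 10% / 15% |
| All increasers removed | 0.6% / 6% | 6% / 35% | 35% / 88% |
| All increasers comply, recorded as unchanged | 0.6% / 6% | 6% / 35% | 35% / 88% |

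The last two rows agree because only the number of reducers matters once no increase remains in the data. The first row stays at or below the nominal 2.5% per tail, so the excess comes from the rule and not from the test.

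**Direction without significance.** If no increase remains, the observed mean falls below zero as soon as one patient reduces. That has probability 1−(1−p)^n: 54% / 79% at p = 5%, and 79% / 96% at p = 10%.

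**Multiplicity.** Section 2.5.1.2 applies Holm-Bonferroni without stating the number of tests. Assuming four, the strictest step is 0.05/4 = 0.0125. At p = 20% with all increasers removed, the rate falls from 35% / 88% to about 6% / 57%. The bias in the mean stays at −0.250.

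**The case against.** A reader might infer that every patient whose use rises is removed and that the trial will therefore report a significant reduction. The documents do not support that, for these reasons:

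- **Only significant rises lead to withdrawal.** The example given is a medication or therapy not used before. Taking more of an existing analgesic is forbidden, but the text does not clearly make it a ground for withdrawal. Such rises can stay in the data.
- **Withdrawal from the study is not stated to mean exclusion from the analysis.** The follow-up review of treatments is where an escalation would be noted. The plan is silent on what happens to that record, so dropping it is plausible but not specified.
- **The drift rates are assumed.** At 5% each way, or with partial removal, the false-reduction rates are modest. If nobody changes medication, the rate is zero.
- **The test is assumed**, and the Holm adjustment lowers every rate in the table.

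All four points limit the size, and they stand. None removes the bias. Rises are forbidden and falls are not, so any baseline-to-endpoint summary is shifted towards reduction if some patients would otherwise have increased, and Holm does not alter an estimate. The protocol's one built-in increase, "Anti-inflammatory medications will also begin 1 day prior to and up to 7 days after the procedure", ends within about a week and does not offset the bias at 6 months.

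It is also fair to say that counting withdrawn patients leaves part of the problem in place, because compliant patients who needed more are still recorded as unchanged. The fix therefore includes a caveat as well as a change of analysis.

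**Conclusion.** The point holds as a bias of certain direction and unknown size. The direction requires only that some patients would have increased their medication without the rule. On the assumptions above, the false-reduction rate runs from about 0.6% (15 patients) and 6% (30 patients) at 5% drift each way to 35% and 88% at 20%, if no increase stays in the data. With half of the increasers removed it is 3% and 9% at 10% drift, and 10% and 15% at 20%. Holm adjustment would lower these rates.

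The stronger statement, that a reduction will be shown whatever embolization does, is not supported: it needs frequent drift and near-complete suppression or removal of increases, and the documents establish neither. The medication finding affected here is a secondary outcome and a named objective. This is more than missing detail, because following the plan as written tilts the result.

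**What to change.** Leave the therapy rule to the investigators and change the data and the analysis.

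1. Record analgesic and other knee therapy to 6 months for every treated patient, including those withdrawn for escalation, and list this at the follow-up visits.
2. In Section 2.5.1.2, define medication change as increased, unchanged or decreased, with all treated patients as the denominator. Count every escalation, and every withdrawal for escalation, as increased.
3. Report the number who escalated, and the proportion decreased minus the proportion increased with its 95% CI.
4. State in Section 2.5.1.2 that subjects were told not to escalate, that increases suppressed by compliance cannot be recovered, and that a fall in medication use is not by itself evidence of an effect of embolization.
5. Reconcile the escalation paragraph in Section 2.4.2.1 with the withdrawal list below it.

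Steps 1 to 3 correct the part due to withdrawal: if every increaser is recorded as such, the expected difference without an effect returns to p − p = 0. They do not correct the part due to compliance, where it stays at p in favour of reduction; only step 4 deals with that. The cost is some wording, added medication recording at follow-up including a few withdrawn patients, and a smaller reported reduction.
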